5.3.9 Neurologic Assessment

The incidence of new clinically detectable neurological events or deficits, or any comparative change in indices of higher cognitive function following implantation of the Evolut R system in the treatment of patients with symptomatic severe aortic stenosis is an important clinical endpoint. Per the VARC-2 guidelines, it is recommended to complete mRS assessments at baseline, all scheduled visits and at 90 days after onset of any confirmed or suspected neurological event (see Table 3). The mRS will be used to classify non-disabling versus disabling stroke in accordance with the VARC-2 definitions. In addition, it is recommended to use neuroimaging to assess the etiology of the stroke.

Confirmed or suspected strokes (disabling and non-disabling) meeting the VARC-2 criteria should be reported as Serious Adverse Events (SAEs) according to the requirement in section 5.7.

5.3.10 Vital Status

A vital status (alive or deceased) should be confirmed for trial subjects at trial exit and recorded on the appropriate e-CRF.

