5.2.1 Study Visit Requirements Matrix

The following table indicates the parameters expected to be routinely evaluated by investigational sites.

Table 3: Schedule of assessments

Data Collection Requirement	Assessment Intervals						
	Baseline ⁵	Implant	Discharge	30 Days ⁵	1 Year ⁵	2 & 3 Years ⁵	Study Exit
Heart Team Assessment ¹	X						
Informed Consent (either patient Informed Consent or Data Release Form)	X						
Demographics and Medical History	X						
Physical Examination	X		X	X	X	X	
NYHA Classification	X			X	X	X	
Risk scores (STS risk score, Log. EuroSCORE and EuroSCORE II)	X						
Katz ADL	X						
Relevant Medications	X		X	X	X	X	
MSCT	X ²						
Transthoracic Echo (TTE)	X		X ³		X		
12-lead ECG	X		X	X	X	X	
Operative Information		X					
Modified Rankin Score ⁴	X		X	X	X	X	
Adverse Events/ Device Deficiency	X	X	X	X	X	X	
Vital Status							X

Notes

- Heart Team assessment documentation required for enrolled subjects who are <80 years of age and have a STS predicted risk of mortality of <8%.
- Pre-implant MSCT should be within 365 days of index procedure.
- It is recommended to perform TTE for device success within 24 hours to 7 days post-procedure
- Modified Rankin Score to be performed at 90 days following any stroke as well.
- Patients are followed per standard of care, therefore there are no mandatory visit windows defined in this study, however the visit windows defined below are provided as recommendation and guidance.
 - Baseline Within 10 weeks prior to index procedure (except for TTE and MSCT)
 - 30 Days Between 30 and 60 days post procedure
 - 1 Year Between 365 and 425 days post procedure
 - 2 Years Between 730 and 790 days post procedure
 - 3 Years Between 1095 and 1155 days post procedure

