5.3 Trial Assessments

5.3.1 Relevant Medications

Use of the following medications will be collected at baseline and at each postoperative interval and recorded on the appropriate e-CRF:

- Anticoagulants
- Antiplatelets
- Aspirin (including Carbasalate calcium)

The Investigator's standard clinical practice will determine the appropriate anti-thrombotic medication use for each subject.

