5.4.2 Lost To Follow-Up

The subject may only be considered lost to follow-up after all efforts to obtain compliance are exhausted. At a minimum, four attempts must be made to contact the subject and documented in the subject's trial records:

- 3 telephone attempts to the subject's last known phone number, and if unsuccessful,
- 1 certified letter from the PI to the subject's last known address

If the site is unable to reach the subject after the documented attempts, the site should make every attempt to verify the subject's vital status (alive or deceased).

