3.3. Handling of Dropouts and Missing Data

Every effort will be undertaken to minimize missing data. In time-to-event outcomes drop-outs will be censored at the time of discontinuation, consistent with the Kaplan-Meier approach.

Unless otherwise specified in each objective, no statistical techniques will be used to impute missing data for continuous or categorical outcomes. If a subject's data are missing for any reason, that subject will not be included in that portion of the analysis. The number of subjects included in each analysis will be reported so that the reader can assess the potential impact of missing data.

In the case of partial dates, if only the month and year are known, the event or assessment will be analyzed as if it occurred on the 15th of that month. If only the year is known, the event or assessment will be analyzed as if it occurred on June 30th of that year. These resolutions of partial dates are subject to the restrictions that pre-procedure events and assessments must occur between the enrollment date and the procedure date and post-procedure events and assessments must occur no earlier than the procedure date.

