3.5. Kaplan-Meier Analyses

In the Kaplan-Meier analysis, the product-limit estimate of the event rate, the number of subjects at risk, the number of subjects with events, the Peto standard error of the estimate, and the loglog transformed 95% confidence interval using the Peto standard error at 1 month (30 days), 1 year (365 days), 2 years (730 days) and 3 years (1095 days) will be presented.

For subjects without an event, the date of censoring will be the latest date of all follow-up visits, assessments, and events (including death in those objectives where death is not the endpoint).

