3.7.3.4. Data Collection and Analysis Methods

The CEC codes for the VARC-2 Combined Safety Endpoint:

- All-cause mortality (CEC Death Form)
- All stroke (disabling and non-disabling) (CEC: 102 to 107)
- Life-threatening bleeding (CEC: 110)
- Acute kidney injury: stage 2 or 3 (including renal replacement therapy) (CEC: 114 to 115)

- Coronary artery obstruction requiring intervention (CEC: 152)
- Major vascular complication (CEC: 120 to 127)
- Valve-related dysfunction requiring repeat procedure (BAV, TAVI, or SAVR)
 - Catheter intervention to repair or replace Evolut R
 - Surgery intervention on Evolut R

As described in section 3.5, a Kaplan-Meier analysis will be performed for the VARC-2 Combined Safety Endpoint at 30 days post-procedure and for each individual component. These objectives will be analyzed for the safety analysis set defined in section 3.4.

3.7.4. Secondary Objective #5 (Safety) - Event Rate of New Permanent Pacemaker Implant at 30 Days

This objective is to characterize the event rate of new permanent pacemaker implant at 30 days.

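### The Kaplan-Meier censoring rule can credit event-free time for non-fatal endpoints from a date on which only vital status was known

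*Protocol*

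**What the plan says.** SAP 3.5 states that, for a subject without an event, "the date of censoring will be the latest date of all follow-up visits, assessments, and events". Its parenthesis adds death as such a date where death is not the endpoint, so the rule is meant for non-fatal endpoints too.

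SAP 3.7.3.4 applies it to the safety endpoints: "a Kaplan-Meier analysis will be performed for the VARC-2 Combined Safety Endpoint at 30 days post-procedure and for each individual component". SAP 3.7.4.4 does the same for new pacemaker at 30 days.

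The SAP does not define an assessment. The protocol puts Vital Status (5.3.10) under the heading "5.3 Trial Assessments" and gives it a row, in the study-exit column, of "Table 3: Schedule of assessments". The instruction itself is "A vital status (alive or deceased) should be confirmed for trial subjects at trial exit and recorded on the appropriate e-CRF". Where telephone calls and a certified letter have failed, Protocol 5.4.2 says "the site should make every attempt to verify the subject's vital status (alive or deceased". It asks for no adverse-event information at that step.

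SAP 3.3 carries a second censoring statement: "In time-to-event outcomes drop-outs will be censored at the time of discontinuation, consistent with the Kaplan-Meier approach".

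**The concern.** A check that a subject is alive is valid follow-up for mortality. It says nothing about whether the subject has had a stroke, a bleed, a repeat procedure or a pacemaker. If its date is used to censor those endpoints, the subject stays in the risk set as event-free over a period in which events were not ascertained. Unknown is then counted as absent. The rate is pulled down, the number at risk is too large, and the Peto standard error that SAP 3.5 specifies is too small.

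The direction favours the device. The safety secondary objectives are descriptive with no hypothesis test, so these estimates are themselves the result.

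**Working it through.** **The plan's own figure.** The documents give no expected rate or sample size for any non-fatal endpoint. The one computed figure is the 934 evaluable subjects for 30-day mortality (SAP 3.6.4: 7.3% against 10.0%, one-sided 0.05, 90% power). An exact binomial search reproduces it: 934 is the smallest n reaching 90%, with a critical value of 78 deaths, actual alpha 0.0493 and power 0.901. It involves no non-fatal endpoint, so nothing below changes it.

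**Who is affected at 30 days.** Only a subject whose last adverse-event review was before day 30, who was later verified alive, and whose later event went unreported. A subject seen at a 30-day visit on or after day 30 is not affected. Acute kidney injury is defined only up to day 7 (Protocol Appendix E), so that component is barely touched.

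**Formula.** Let p be the true 30-day rate, f the share of events falling after the last event review, and m the share of subjects known only to be alive from then on. If loss is unrelated to event risk:

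- early events, all seen: p(1 − f)
- late events, seen in the remaining subjects only: (1 − m) × p × f
- reported rate: p(1 − f) + (1 − m)pf = p − m × f × p

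The understatement is therefore m × f × p.

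**Results for an assumed p = 10%** (m and f also assumed):

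- m 1%, f 25%: 0.01 × 0.25 × 10 = 0.025 points
- m 2%, f 25%: 0.05 points
- m 7%, f 25%: 0.175 points
- m 7%, f 50%: 0.35 points

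At p = 5% these halve, and at p = 20% they double. If unreachable subjects carry k times the usual risk, multiply by about k.

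**Simulation check** (1000 subjects, last event review at day 7, m 7%, 300 runs). The first figure censors at the last event review, the second at the alive-only date:

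- true 5%, f 25%: 4.98% and 4.90%
- true 10%, f 25%: 10.03% and 9.86%
- true 20%, f 25%: 19.96% and 19.62%
- true 20%, f 50%: 20.09% and 19.39%

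The gaps agree with the formula. Censoring at the last event review recovers the true rate to within simulation error.

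**Standard error.** The Peto standard error varies with one over the square root of the number at risk. If a share m is wrongly at risk, it is too small by a factor of about √(1 − m). At m = 7%, √0.93 = 0.964, or about 3.6% too small.

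**Scale.** With 1000 subjects and p = 10%, the 95% half-width is about 1.96 × √(0.1 × 0.9/1000) = 1.86 points. The range of 0.025 to 0.35 points is about 1% to 19% of that.

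**The case against.** Five points can be made in the plan's defence.

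- **Vital status is not named in SAP 3.5.** Treating it as an assessment is an inference from a protocol heading and a table title. That is true, though it is the natural reading, and the opposite reading also causes trouble. SAP 3.6.2 builds the primary denominator on the same wording. If vital status is excluded there, a subject verified alive after day 30 without a later visit counts as missing for mortality. One undefined term cannot serve both kinds of endpoint.
- **SAP 3.3 already deals with drop-outs, and Protocol Table 5 ends follow-up for lost or withdrawn subjects at death, withdrawal or the last completed visit.** So a reader who infers that 3.5 is the only censoring rule is wrong. But 3.3 and 3.5 are not reconciled, and discontinuation can itself be dated after the last event review. Table 5 sets required follow-up; it is not a censoring rule.
- **Events may be known anyway.** Sites must report serious and VARC-2 events until follow-up is complete (Protocol 5.7.2). Local-hospital and telephone information is accepted (5.2.5), and ordinary contacts collect adverse events (5.4.1). This stands: it limits the number affected and rules out saying that nothing is known after discharge.
- **The plan's 7% attrition does not size the group.** A reader might infer that up to 70 of 1000 subjects are wrongly at risk at day 30. The 7% is loss from evaluable status for mortality. If a vital-status date counts, a subject verified alive on or after day 30 is evaluable under SAP 3.6.2 and so is not part of that 7%. Above, 7% is only the top of an assumed range.
- **Later time points are not specified for these endpoints.** A reader might infer a larger bias at one to three years because SAP 3.5 lists those times. The components and pacemaker are specified at 30 days only; SAP 3.6.2 gives later rates for mortality.

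**Conclusion.** The concern holds as a weakness of wording with a small, one-directional effect. Followed as written, SAP 3.5 can give event-free credit that was never ascertained for non-fatal endpoints, and SAP 3.3 does not clearly prevent it. The 30-day rates can be understated; the documents do not show that they will be.

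For an assumed true rate of 10%, the size is roughly 0.03 to 0.35 points over m of 1–7% and f of 25–50%. All three quantities are assumptions, and the formula takes loss to be unrelated to event risk. The effect would be larger only if loss were heavier or concentrated in higher-risk subjects.

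The primary mortality test and its sample size are unaffected, because a date known alive is valid follow-up for death. The case for acting is that the bias favours the device and is cheap to remove before analysis.

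**What to change.** State one reconciled rule across SAP 3.3 and 3.5:

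- **All-cause mortality:** censor at the latest date known alive from any source, including vital status.
- **Non-fatal components and new pacemaker:** censor at the last visit or contact at which adverse events were reviewed, or at death where death is not the endpoint. Ignore dates that carry vital status only.
- **Composite:** count deaths from any source, use the same event-review censoring for the non-fatal part, and report the present rule as a sensitivity analysis. The composite should not stay on the old rule while its components change, since their risk sets would then differ. Counting late deaths while censoring survivors earlier can tilt the composite slightly upward, which is a further reason to show both.

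The cost is about two sentences in the SAP and one derived date in the programs. The downside is slightly higher reported rates and slightly wider intervals.

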5.4 Subject Accountability

5.4.1 Missed Follow-up Visit

The Investigator should make every effort to contact the subject preferably within the visit window, to collect the subject's vital status as well as information related to potential adverse events, safety data, and hospitalizations.

As only standard of care data are being collected, subjects cannot miss study-specific visits. In case no standard of care visit has taken place in the pre-specified follow-up interval period, sites should conduct a telephone follow-up visit just prior to the closure of the visit window. Up to 3 attempts and any information received during a telephone follow-up should be filed as source documentation by the sites. If the subject cannot be reached by phone, the visit should be considered missed and, if applicable a protocol deviation must be completed, as outlined in section 5.8.

5.4.2 Lost To Follow-Up

The subject may only be considered lost to follow-up after all efforts to obtain compliance are exhausted. At a minimum, four attempts must be made to contact the subject and documented in the subject's trial records:

- 3 telephone attempts to the subject's last known phone number, and if unsuccessful,
- 1 certified letter from the PI to the subject's last known address

If the site is unable to reach the subject after the documented attempts, the site should make every attempt to verify the subject's vital status (alive or deceased).

5.4.3 Subject Withdrawal

All subjects will be encouraged to remain in the study through the last follow-up visit at three years and up to 5 years, if the study is extended based on clinical assessments during the course of the study. Subjects who discontinue participation prematurely will be included in the analysis of results (as appropriate) but they will not be replaced in the enrollment of total study subjects. If a study subject is discontinued from the study early, the reason for discontinuation should be documented in the subject file and a Study Exit e-CRF must be completed. If discontinuation is because of safety or lack of effectiveness, the patient shall be asked to be followed for collecting safety data outside the clinical study.

Once a subject has been enrolled in the study (i.e. written Informed Consent has been obtained) he/she may withdraw his/her consent to participate in the study at any time without prejudice. Participation in this study is entirely voluntary.

If a subject discontinues the study at any time, is withdrawn from the study early, or completes all follow-up visits they should continue to be followed-by the implanting center according to their standard clinical practice for transcatheter aortic valve patients.

5.4.4 Subject Disposition

The Investigation site will maintain a log of all subjects enrolled in the clinical study, assigning an identification code linked to their names, alternative subject identification or contact information.

There are several scenarios in which a subject may exit the trial. Table 5 below details how the data will be handled for each scenario.

Table 5. Trial Exit Scenarios

Scenario	Follow-up Required	e-CRFs Required
Subject enrolled, but no implant attempted (i.e. not taken to the procedure room for implantation)	None	
 ▪ Inclusion/Exclusion e-CRF ▪ Baseline e-CRF (as applicable) ▪ AE e-CRF (as applicable) ▪ Trial Exit e-CRF
Subject enrolled, implant attempted (i.e. taken to the procedure room), but the subject does not receive the Evolut R TAV	30 days post-attempted implant for safety only	
 ▪ Inclusion/Exclusion e-CRF ▪ Baseline e-CRF (including TTE) ▪ Implant e-CRF ▪ Discharge e-CRF ▪ 30 Day e-CRF ▪ AE e-CRF (as applicable) ▪ Trial Exit e-CRF
Subject enrolled, implanted with Evolut R TAV, and has his/her valve explanted	Discharge following explant hospitalization or 30 days post implant (whichever comes later).	
 ▪ All required e-CRFs through last visit completed ▪ Surgical Reintervention e-CRF ▪ AE e-CRF (as applicable) ▪ Trial Exit e-CRF
Subject enrolled, implanted with Evolut R TAV, and exits the trial early due to any of the following: 
 ▪ Lost to Follow-up ▪ Death ▪ Withdrawal 	Through point of death, withdrawal, or last visit completed	
 ▪ All required e-CRFs through last visit completed ▪ AE e-CRF (as applicable) ▪ Trial Exit e-CRF
Subject enrolled, implanted and completes the trial requirements	Through 3 year follow-up	
 ▪ All required e-CRFs ▪ AE e-CRF (as appropriate) ▪ Trial Exit e-CRF

5.5 Role of the sponsor’s representatives

Representatives from Medtronic may provide technical support during the implant procedures to the implanting physicians and study center staff relative to the use of the Evolut R system. This activity will be performed under supervision of the Principal Investigator and will not bias the data integrity in any

way. The sponsor representatives providing technical support shall be listed on the Sponsor Technical Support List.

5.6 Source documents

Entered data must be traceable to source documents. Source documentation is defined as the first time the data appear and may include all clinical records, hospital records, procedural reports, autopsy reports, and any other material that contains original information used for study data collection or adverse event reporting.

The e-CRFs may not serve as source documents. Source documentation for data elements not routinely captured in medical records (e.g. echocardiography variables, Modified Rankin Score, risk score calculators) may vary from center to center: the site may use technical worksheets if identified as source documents. Worksheets need to be signed and dated by the Principal Investigator or a delegated Investigator.

Data reported on the e-CRFs should be traceable to source documents. Source documents must be available for review by Medtronic personnel and/or applicable regulatory agencies or EC/IRB and will be used for verification of the data reported on the e-CRFs and adjudication of AEs.

Where copies of the original source document as well as print outs of original electronic source documents are retained, these shall be signed and dated by a member of the investigation site team with a statement that it is a true reproduction of the original source document.

The Investigator must ensure the availability of source documents from which the information on the e-CRFs was derived. In addition, the medical records of study subjects should be marked or flagged in such a way to indicate their participation in the study. For Investigational sites in Sweden, the investigator should also provide a short explanation on the clinical study in the patient medical files.

5.7 Adverse events and Device Deficiencies

5.7.1 Definition/classification

For the purposes of the clinical report, Medtronic will classify each adverse event according to ISO 14155:2011 (Table 6).

Where the definition indicates “device”, it refers to any component of the Evolut R system used in the study.

Table 6. Adverse Event Definitions

Adverse Event (AE): (ISO14155:2011 3.2)
 
Any untoward medical occurrence, unintended disease or injury, or untoward clinical signs (including abnormal laboratory findings) in subjects, users or other persons, whether or not related to the investigational medical device
 
NOTE 1: This definition includes events related to the investigational medical device or the comparator.

NOTE 2: This definition includes events related to the procedures involved.

NOTE 3: For users or other persons, this definition is restricted to events related to investigational medical devices.

Adverse Device Effect (ADE): (ISO14155:2011 3.1)

Adverse event related to the use of an investigational medical device

NOTE 1: This definition includes adverse events resulting from insufficient or inadequate instructions for use, deployment, implantation, installation, or operation, or any malfunction of the investigational medical device.

NOTE 2: This definition includes any event resulting from use error or from intentional misuse of the investigational medical device

Serious Adverse Event (SAE): (ISO 14155:2011 3.37)

An adverse event that

- a) led to death,
- b) led to serious deterioration in the health of the subject, that either resulted in
 1. a life-threatening illness or injury, or
 2. a permanent impairment of a body structure or a body function, or
 3. in-patient or prolonged hospitalization, or
 4. medical or surgical intervention to prevent life-threatening illness or injury or permanent impairment to a body structure or a body function,
- c) led to foetal distress, foetal death or a congenital abnormality or birth defect.

NOTE: Planned hospitalization for a pre-existing condition, or a procedure required by the CIP, without serious deterioration in health, is not considered a serious adverse event.

Serious Adverse Device Effect (SADE): (ISO 14155:2011 3.36)

Adverse device effect that has resulted in any of the consequences characteristic of a Serious Adverse Event.

Unanticipated Serious Adverse Device Effect (USADE): (ISO 14155:2011 3.42)

Serious adverse device effect which by its nature, incidence, severity or outcome has not been identified in the current version of the risk analysis report

NOTE: Anticipated serious adverse device effect (ASADE) is an effect which by its nature, incidence, severity or outcome has been identified in the risk analysis report.

Device deficiency: (ISO 14155:2011 3.15)

Inadequacy of a medical device with respect to its identity, quality, durability, reliability, safety or performance

NOTE: Device deficiencies include malfunctions, use errors, and inadequate labelling.

An event is not considered an AE if it has been identified as a pre-existing condition, unless there is a change in nature, severity or degree of incidence of the event.

